2.4 Protocol deviations

The FAS will be used for the protocol deviation summary tables and listings. The frequency counts and percentage of patients with any CSR-reportable protocol deviation will be tabulated by the deviation category (entry criteria not satisfied; wrong treatment or incorrect dose; developed withdrawal criteria, but not withdrawn; took an excluded concomitant medication; others). The full list of protocol deviations are documented in the Study Specification Document (SSD).

2.5 Treatments (study treatment, rescue medication, other concomitant therapies, compliance)

Unless otherwise noted, the Safety set will be used for all treatment/medication data summaries and listings.

2.5.1 Study treatment

2.5.1.1 Dose intensity and exposure

For Arm A and C (monotherapy):

Last date of exposure to study treatment is:

- ✓ min(the last date of study treatment + 13 days, death date, data cut-off date) for Q2W schedule
- ✓ min(the last date of study treatment + 27 days, death date, data cut-off date) for Q4W schedule

For Arm B (combo therapy):

Last date of exposure to study treatment is:

- ✓ min(max(last date of PDR001 administration, last date of LAG525 administration) + 13 days, death date, data cut-off date) for Q2W schedule
- ✓ min(max(last date of PDR001 administration, last date of LAG525 administration) + 20 days, death date, data cut-off date) for Q3W schedule
- ✓ min(max(last date of PDR001 administration, last date of LAG525 administration) + 27 days, death date, data cut-off date) for Q4W schedule
- ✓ min(max(last date of PDR001 administration + 27 days, last date of LAG525 administration + 13 days), death date, data cut-off date) for LAG525 Q2W and PDR001 Q4W schedule

Definitions are as follows:

- Duration of exposure to study treatment (weeks): (last date of exposure to study treatment – first date of study treatment + 1)/7 (periods of interruption are not excluded)
- Duration of exposure to study drug (weeks): (last date of exposure to study drug – first date of study drug + 1)/7 (periods of interruption are not excluded)
- Actual cumulative dose (mg): total actual dose for the study drug over the duration for which the patient is on study treatment as documented in the DAR eCRF.

The following algorithms will be used to calculate the actual dose per one infusion in mg:

- ✓ For weight based dosing: Actual dose (mg) = (Calculated dose prescribed, mg) × (Total volume administrated, ml) / (Total volume constituted, ml)
- ✓ For flat dosing: Actual dose(mg) = (Dose prescribed, mg) × (Total volume administrated, ml) / (Total volume constituted, ml)

These parameters used for calculation ('Calculated dose prescribed', 'Dose prescribed', 'Total volume constituted', 'Total volume administered') will be collected on the DAR eCRF page. For patients who did not take any of study treatment, the actual cumulative dose is by definition equal to zero. Actual cumulative dose will then be calculated as the sum of actual dose per one infusion for all infusions.

- Planned cumulative dose (mg): the total dose planned to be given as per the protocol up to the last date of study treatment administration. It is calculated in mg as:
 - ✓ For weight based dosing: Planned cumulative dose (mg) = sum of (Calculated dose prescribed, mg) for all infusions
 - ✓ For flat dosing: Planned cumulative dose (mg) = sum of (Dose prescribed, mg) for all infusions.

Similarly, 'Calculated dose prescribed' and 'Dose prescribed' will be collected on the DAR eCRF page. The planned cumulative dose is not summarized/listed. It is used for relative dose intensity calculations.

- DI (mg/day): actual cumulative dose (mg) / duration of exposure (days) for patients with non-zero duration of exposure.
- PDI (mg/day): planned cumulative dose (mg)/duration of exposure (days)

The dose intensity (DI) and planned dose intensity (PDI) will not be summarized/listed. They are used for relative dose intensity calculations.

- RDI (%): $100 \times \text{DI (mg/day)} / \text{PDI (mg/day)}$

The duration of exposure to study treatment will be summarized. In addition, RDI (including categories: <0.5 , ≥ 0.5 - <0.75 , ≥ 0.75 - <0.9 , ≥ 0.9 - <1.1 , ≥ 1.1) will be summarized for each study drug.

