#### **6.2.3.2.1 Switch to LAG525 in combination with PDR001 for patients treated with LAG525 single-agent**

Upon disease progression, patients assigned to LAG525 monotherapy during dose escalation may switch to LAG525 + PDR001 at a combination dose level that uses the patient's same LAG525 dose and has been determined safe and tolerable in previous dose escalation patients. If there is no combination dose level that includes the patient's LAG525 monotherapy dose, the patient may receive a lower dose level of LAG525 when switching to LAG525 in combination with PDR001; alternatively, the patient may switch to the LAG525 + PDR001 recommended Phase II dose, once the RP2D has been established. Patients switching to combination therapy must have completed at least 4 cycles of LAG525 monotherapy with no toxicity of CTCAE grade  $\geq 2$  considered related to study treatment.

PDR001 may be added to LAG525 treatment only after documented discussion and agreement between Novartis and the Investigator, based on each patient's condition and review of the planned dose and schedule.

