1.1 Study design

This study is a phase I/II, multi-center, open-label study which consists of 3 dose escalation parts (Arms A, B and C) with a staggered start, each followed by a Phase II part.

[figure not shown]
The first escalation is conducted with single-agent LAG525 in advanced solid tumors. The second dose escalation part is performed with the combination of LAG525 and PDR001 in advanced solid tumors. A separate Japanese dose escalation (Arm C) is performed in order to ensure that the safety and pharmacokinetic profiles of single-agent LAG525 are adequately characterized in Japanese patients at more than one LAG525 dose. Arms A and B are followed by a Phase II part after the determination of MTD/RP2D of single-agent LAG525 and combination of LAG525 and PDR001 respectively.

If the RP2D of single-agent LAG525 are the same in Arms A and C, patients enrolled in Japan could be recruited in Phase II single-agent part of the study. In addition, if the recommended dose of PDR001 for Japanese patients on the PDR001X1101 study are the same as that determined in study PDR001X2101, patients in Japan could also enter the combination parts of the study at whichever dose was being tested at that time.

Upon disease progression, patients assigned to LAG525 monotherapy during dose escalation may switch to LAG525 + PDR001 at a combination dose level that uses the patient's same LAG525 dose (or less) and has been determined safe and tolerable in previous dose escalation patients. If there is no combination dose level that includes the patient's LAG525 monotherapy dose, the patient may receive a lower dose level of LAG525 when switching to LAG525 in combination with PDR001;

The study design is summarized in [Figure 1-1](#).

Figure 1-1

Note: In the single agent LAG525 dose escalation (Arm A) at least 21 patients are required to define the RP2D; in the combination dose escalation (Arm B) at least 15 patients are required to define the RP2D and in the Japanese single agent LAG525 dose escalation (Arm C) at least 12 patients are required to define the RP2D.

The final clinical study report (CSR) will be based on all patients’ data from both phase I and phase II parts.

As antitumor activity was not observed with LAG525 single agent but was seen at several dose levels of LAG525 in combination with PDR001, it was decided that only the combination portion of Phase II would be enrolled.

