2.1.1 General definitions

Study drug and study treatment

For Arm A and C (monotherapy):

Study drug and study treatment both refer to LAG525 and are used interchangeably.

For Arm B (combo therapy):

Study drug refers to the individual compound i.e., LAG525 or PDR001. Study treatment refers to any combination of study drugs.

Date of first/last administration of study drug and study treatment

The date of first (last) administration of study treatment is derived as the first (last) date when a non-zero dose of any component of study treatment was administered and recorded on the Dosage Administration Record (DAR) eCRF. For the sake of simplicity, the date of first (last) administration of study treatment will also be referred as start (last) date of study treatment.

Study day

The study day for all assessments/events will be calculated using the start date of study treatment as reference. For assessments/events occurring on or after the start date of study treatment, study day will be calculated as:

Study day (days) = Event date – Start date of study treatment + 1.

Therefore, the first day of study treatment is study day 1.

For all assessment/events occurring prior to the start of the study treatment, study day will be negative and will be calculated as:

Study day (days) = Event date – Start date of study treatment.

Study day will be displayed in the data listings.

On-treatment assessment/event

An on-treatment assessment/event is defined as any assessment/event obtained in the time interval from the start date of study treatment until the last date of study treatment (i.e., including combination partner) + 30 days inclusive.

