2.8 Safety evaluation

The assessment of safety is based on the type and frequency of Adverse Events (AEs) as well as on the number of laboratory values that fall outside of pre-determined ranges (Common Toxicity Criteria for Adverse Events (CTCAE) grading limits or normal ranges as appropriate). Other safety data include electrocardiogram and vital signs.

The Safety set is used for summaries and listings of safety data with the exception of dose limiting toxicities (DLT) for which the DDS is used.

Differences between treatment received and intended treatment, if any, are provided in a listing.

The overall observation period is divided into three mutually exclusive segments:

1. Pre-treatment period: from day of patient's informed consent to the day before first dose of study medication,
2. On-treatment period: from day of first dose of study medication to 30 days after last dose of study medication,

3. Post-treatment period: starting at Day 31 after last dose of study medication.

Safety summaries are primarily based on all data from the on-treatment period. Following last administration of study medication, adverse events (including serious adverse events), and new antineoplastic therapies are collected for a period of 150 days. Following start of new antineoplastic therapy, only study treatment related adverse events are collected. Select summaries of related adverse events are produced for the overall period starting from the first dose of study treatment until the end of the post-treatment period.

All safety assessments are listed and those collected during the post-treatment period are flagged.

For patients who switch from single-agent LAG525 to combination with PDR001, the on-treatment period is defined from day of first dose of study medication to 30 days after the last dose of single-agent LAG525.

All safety assessments from these patients are listed and the assessments performed under combination and those collected 30 days later than the last dose of single-agent are flagged separately.

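### SAP 2.5.1.1 has no cut at the switch to LAG525+PDR001, so read literally the single-agent duration of exposure includes combination time

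*SAP*

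**What the plan says.** SAP 2.5.1.1 ends exposure in Arms A and C at "min(the last date of study treatment + 13 days, death date, data cut-off date) for Q2W schedule" and at "min(the last date of study treatment + 27 days, death date, data cut-off date) for Q4W schedule". Death and data cut-off are the only caps.

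SAP 2.1.1 supplies the terms. For the monotherapy arms, "Study drug and study treatment both refer to LAG525 and are used interchangeably". The last administration is the last "date when a non-zero dose of any component of study treatment was administered and recorded on the Dosage Administration Record (DAR) eCRF".

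SAP 1.1 allows that, at progression, "patients assigned to LAG525 monotherapy during dose escalation may switch to LAG525 + PDR001". Protocol 6.2.3.2.1 adds a condition: "Patients switching to combination therapy must have completed at least 4 cycles of LAG525 monotherapy". Under SAP 2.2 a patient is classified in the Safety Set by assigned treatment if it was received at least once, and SAP 2.5 uses the Safety Set for treatment summaries. Switchers therefore stay in the single-agent group.

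Other parts of the plan do separate the switch:
- SAP 2.8, for safety: "the on-treatment period is defined from day of first dose of study medication to 30 days after the last dose of single-agent LAG525".
- SAP 2.7.2 censors efficacy at the last adequate assessment before the switch.
- Protocol 10.1.4 keeps DLTs after the switch out of the dose-escalation model.
- Protocol 6.2.3.2.1 keeps responses after the switch out of the ORR.

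Neither Protocol 10.3 nor SAP 2.5.1.1 and 2.5.1.2 has a matching rule for exposure, dose intensity, interruptions or reductions.

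**The concern.** A switcher's last LAG525 dose is normally a combination dose. If exposure runs to that dose plus 13 or 27 days, the table labelled single agent reports time on two drugs as time on one.

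Two things are at stake. First, the exposure table and the adverse-event table for the same group would cover different periods, because adverse-event counting stops 30 days after the last single-agent dose. A reader relating events to exposure would be using mismatched time. Second, tolerability (interruptions, reductions, dose intensity) is a secondary endpoint. Dose changes made while a patient was receiving PDR001 could be attributed to LAG525 alone.

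**Working it through.** The documents give no exposure figure to reproduce, so the check applies the SAP's formulas to an assumed patient.

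**Duration of exposure.** SAP 2.5.1.1: weeks = (last date of exposure − first date + 1)/7. Assume Q2W dosing without delays, 4 cycles of 28 days on monotherapy (the minimum before a switch), then k combination cycles.
- Monotherapy doses fall on Days 1, 15, …, 99. The first combination dose is on Day 113 and the last on Day 99 + 28k.
- Literal rule: (99 + 28k + 13)/7 = 16 + 4k weeks.
- Cut at the last single-agent dose: (99 + 13)/7 = 16 weeks for any k.

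| k (assumed) | Literal rule, weeks | Single agent, weeks | Excess over 16 weeks | Share after switch |
|---|---|---|---|---|
| 2 | 24 | 16 | 50% | 33% |
| 4 | 32 | 16 | 100% | 50% |
| 6 | 40 | 16 | 150% | 60% |

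Q4W gives the same weeks: the last single-agent dose is on Day 85, and (85 + 28k + 27)/7 = 16 + 4k.

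At k = 6 on Q2W, exposure runs to Day 267 + 13 = Day 280, while the safety on-treatment period under SAP 2.8 closes on Day 99 + 30 = Day 129.

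**RDI.** SAP 2.5.1.1 defines RDI = 100 × (actual cumulative dose/duration) ÷ (planned cumulative dose/duration). Duration cancels, leaving 100 × actual/planned, with both sums taken over every infusion. Assume 8 full monotherapy infusions and 12 combination infusions, 2 of them half given:
- all infusions: (8 + 10 + 2 × 0.5)/20 = 19/20 = 95%, whether duration is 112 or 280 days;
- single-agent infusions only: 8/8 = 100%.

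Post-switch dosing thus reaches RDI through the infusion sums, not through the exposure end date.

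**Interruptions and reductions.** SAP 2.5.1.2 derives these from dosing-record flags and actual doses, with no stop at the switch. SAP 2.8.5 summarises them for tolerability and takes RDI from 2.5.1, but does not say whether the switch cut in 2.8 applies.

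**Size in a group.** The shift in mean exposure = switchers × combination weeks ÷ patients. Protocol Amendment 10 (study status) gives 134 single-agent patients. The other inputs are assumed:
- 5 switchers, 8 weeks: 40/134 = 0.3 week;
- 10 switchers, 24 weeks: 240/134 = 1.8 weeks.

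Phase I results are also reported by dose and schedule. Protocol Table 14-22 shows 3 to 12 evaluable patients per Arm A group at the January 2016 cut-off. One switcher with 24 combination weeks in a group of 4 shifts its mean by 24/4 = 6 weeks. Later enrolment may have enlarged these groups.

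**The case against.** The best defence is that the SAP is silent rather than wrong. The rule is headed as a monotherapy rule and Arm B has its own. Protocol 6.2.3.2.1 has switchers complete an additional end-of-treatment disposition form, which suggests that the single-agent phase is a separate phase. Derivations are delegated to a programming specification and output shells that are not among the documents, and these may already split at the switch. This makes the intended reading plausible, but it does not supply the rule. The headings name arms, and the general on-treatment definition in SAP 2.1.1 runs "until the last date of study treatment (i.e., including combination partner) + 30 days inclusive".

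A second defence concerns tolerability. SAP 2.8.5 sits under 2.8, so its interruption and reduction counts may inherit the switch cut there. That is fair: a reader might infer that the SAP directs combination-period tolerability into the single-agent tables, and the documents do not go that far. A reader might also infer that the late exposure end date distorts RDI. It does not, because duration cancels.

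A third defence is size. The Amendment 08 rationale speaks of a small number of patients, and switching requires progression, at least 4 completed cycles and no related grade 2 or higher toxicity. This stands.

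**Conclusion.** The point holds for duration of exposure: followed as written, the Arm A/C rule counts LAG525+PDR001 time as single-agent time. For RDI, interruptions and reductions the plan leaves the same gap by a separate route, namely uncut infusion sums and uncut dose-change rules. Whether the 2.8 cut governs 2.8.5 is not stated.

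The size is unknown, because the documents give neither the number of switchers nor the time they spent on combination. The 50% to 150% figures are per-patient illustrations. They rest on assumed combination durations of 8 to 24 weeks and on the minimum 16 weeks of monotherapy; after 32 weeks of monotherapy, 24 combination weeks would add 24/32 = 75%. They should not be read as bias in the arm, where the assumed cases give 0.3 to 1.8 weeks. The primary endpoints are not affected, since DLTs and responses after the switch are already excluded. The gap should be closed because it touches a secondary endpoint and is cheap to close.

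**What to change.** - **SAP 2.5.1.1:** for switchers, set the last date of single-agent exposure to the minimum of last single-agent LAG525 dose + 13 days (Q2W) or + 27 days (Q4W), the day before the first PDR001 dose, death, and data cut-off.
- **SAP 2.5.1.1, 2.5.1.2 and 2.8.5:** restrict single-agent actual and planned cumulative dose, RDI, interruptions and reductions to infusions before the first PDR001 dose.
- **Listings:** show post-switch dosing separately and flag it, as the SAP already does for post-switch efficacy and safety data.
- **Table note:** state that the adverse-event window in SAP 2.8 still runs to 30 days after the last single-agent dose. For the assumed patient, exposure would end on Day 112 and the adverse-event window on Day 129 (Q2W, 17 days later) or Day 115 (Q4W, 3 days later). The two windows become close but not identical.

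The cost is a few sentences and one date filter in the exposure datasets, using the first PDR001 date on the dosing record. Reported single-agent exposure becomes somewhat shorter for switchers. No patient's treatment and no data collection changes.

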## **10.3 Treatments (study treatment, concomitant therapies, compliance)**

For each of LAG525 and PDR001, the actual dose and duration in days of treatment as well as the dose intensity (actual dose received/actual duration) and relative dose intensity (the ratio of dose intensity to planned dose/planned duration) will be listed and summarized by means of descriptive statistics by treatment group. Categories for relative dose intensity of LAG525 or PDR001 will be specified as  $< 0.5$ ,  $\geq 0.5 - < 0.75$ ,  $\geq 0.75 - < 0.9$ ,  $\geq 0.9 - < 1.1$  and  $\geq 1.1$ . The number and proportion of patients within each category will be presented by treatment group.

Concomitant medications and significant non-drug therapies prior to and after the start of the study treatment will be listed by patient and summarized by ATC term and treatment group.

The reason for discontinuation from treatment will be summarized and listed, along with dates of first and last dose of LAG525 and PDR001 (if applicable), duration of exposure to LAG525 and PDR001 (if applicable) and date of discontinuation for each patient.

Compliance with the protocol will be assessed by the number and proportion of patients with protocol deviations. Protocol deviations will be identified prior to database lock and will be listed and summarized.

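### As calculated in the SAP, relative dose intensity is mg infused over mg prescribed, so delaying fully infused doses never lowers it, contrary to Protocol 10.3

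*SAP*

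**What the plan says.** Protocol 10.3 defines dose intensity as dose received over actual duration, and promises that "relative dose intensity (the ratio of dose intensity to planned dose/planned duration) will be listed and summarized". Two different durations are involved.

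SAP 2.5.1.1 takes these steps:

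- Actual dose per infusion is the prescribed mg times the fraction "Total volume administrated, ml) / (Total volume constituted, ml". Actual cumulative dose is the sum over all infusions.
- Planned cumulative dose is described in prose as "the total dose planned to be given as per the protocol up to the last date of study treatment administration". The calculation that follows, for flat dosing, is "Planned cumulative dose (mg) = sum of (Dose prescribed, mg) for all infusions". The weight-based version has the same form.
- Dose intensity (DI) is actual cumulative dose over duration of exposure in days. Planned dose intensity (PDI) uses the same denominator: "PDI (mg/day): planned cumulative dose (mg)/duration of exposure (days".
- RDI is 100 × DI / PDI, reported in the categories <0.5, 0.5 to <0.75, 0.75 to <0.9, 0.9 to <1.1 and ≥1.1.
- "The dose intensity (DI) and planned dose intensity (PDI) will not be summarized/listed".

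SAP 2.8.5 uses RDI to assess tolerability, and SAP 2.5.3 reuses its categories for compliance.

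**The concern.** Dose intensity is a named tolerability endpoint among the secondary objectives (Protocol Table 3-1, SAP 1.2). DI itself is not reported, so RDI is the only dose-intensity output. Much of Protocol Table 6-5 handles toxicity by holding treatment and then resuming at an unchanged dose, so lost time is a main way in which poor tolerability would reduce intensity. An RDI that ignores time cannot show this: a patient with repeated holds would be reported at full relative intensity.

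The SAP also disagrees with itself. Its prose for planned dose refers to the protocol schedule, while its formula refers to what was prescribed at each infusion. It withholds DI although Protocol 10.3 says DI will be listed and summarized. It defines RDI in percent but categorises it in fractions, so read literally a value of 85.7 would fall in ≥1.1.

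**Working it through.** The documents state no RDI value, so there is no figure to reproduce. The check is algebra on the SAP formulas, followed by worked dosing histories.

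**Algebra.** For infusion *i*, let pᵢ be the prescribed mg and fᵢ the fraction of the constituted volume given. Let T be duration of exposure.

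- Actual cumulative dose A = Σ pᵢfᵢ; planned cumulative dose P = Σ pᵢ.
- RDI = (A/T) / (P/T) = A/P.

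T drops out whichever duration is meant, because DI and PDI use the same one. If every fᵢ = 1, RDI = 100% whatever the dates. Since fᵢ should not exceed 1, the ≥1.1 category cannot be reached without a data error.

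**Comparators.** Protocol 10.3 does not define planned duration. I assume that the planned rate is the assigned dose per assigned interval τ. For six full doses with k delays of 7 days, RDI = 6τ / (6τ + 7k). The SAP prose is read as six doses divided by the number scheduled up to the last infusion date. Q2W exposure ends 13 days after the last infusion (SAP 2.5.1.1), so on-time dosing has its last infusion on day 71 and 84 days of exposure.

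| 7-day delays (Q2W) | Last infusion | Assigned rate | SAP prose | SAP formula |
|---|---|---|---|---|
| 1 | day 78 | 84/91 = 92.3% | 6/6 = 100% | 100% |
| 2 | day 85 | 84/98 = 85.7% | 6/7 = 85.7% | 100% |
| 3 | day 92 | 84/105 = 80.0% | 6/7 = 85.7% | 100% |
| 4 | day 99 | 84/112 = 75.0% | 6/8 = 75.0% | 100% |
| 5 | day 106 | 84/119 = 70.6% | 6/8 = 75.0% | 100% |

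By the assigned rate, one delay changes no category, two to four delays move the patient down one category, and five move the patient down two.

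**Other histories.**

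- One 21-day hold, Q2W: assigned rate 84/105 = 80.0%; prose 6/7 = 85.7%; SAP formula 100%.
- Q3W: two delays give 126/140 = 90.0% (no category change); three give 126/147 = 85.7%.
- Q4W: two delays give 168/182 = 92.3% (no category change); three give 168/189 = 88.9%.
- Two of six Q2W doses omitted (infusions on days 1, 15, 57 and 71; 84 days of exposure): assigned rate 4 × 14/84 = 66.7%. The SAP gives 4/6 = 66.7% if the dosing record holds prescribed mg for the omitted doses, and 4/4 = 100% if it does not.
- On-time dosing with half the volume given for the last three of six doses: (3 + 1.5)/6 = 75% under all three definitions. Incomplete infusion is what the SAP formula does detect.

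**The case against.** The algebra is hard to dispute; the better objections concern importance and remedy.

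- **The information appears elsewhere.** SAP 2.5.1.2 lists all doses with reasons for change and summarises the number and duration of interruptions and reductions. Protocol 6.3.1 speaks of a late dose as an interruption and requires interruptions to be recorded. SAP 2.5.1.1 adds that "The duration of exposure to study treatment will be summarized". This limits the damage, but it does not correct the RDI used in 2.8.5. SAP 2.5.1.2 also refers to a zero actual dose between non-zero doses, which a late full dose need not produce.
- **Omitted and reduced doses depend on the case report form**, which is not available. This stands, and that part of the point is conditional. The result for delays does not depend on it.
- **The sizes are hypothetical.** This stands. Protocol 7.1 also allows a ±7-day visit window, and 6.1.1 allows a cycle to be extended by 7 days for recovery. A lower RDI would therefore describe delivered intensity, not misconduct or necessarily toxicity.
- **The replacement has its own artefact.** Exposure is cut at death or data cut-off, which can push RDI above 1: cutting 10 days from 84 gives 84/74 = 113.5%, and one Q2W dose followed by death on day 5 gives 14/5 = 280%. This is a real drawback and needs a stated convention.
- **The ratio suits compliance.** This is correct for SAP 2.5.3, which is worded against prescribed doses, but not for tolerability.

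**Conclusion.** The concern holds. As calculated, the SAP's RDI cannot fall because of delays to fully infused doses, and this contradicts both Protocol 10.3 and the SAP's own description of planned dose. In the Q2W illustration, RDI is overstated by 7.7 percentage points after one 7-day delay (100 − 92.3) and by 29.4 after five (100 − 70.6). These figures assume six full doses and a planned rate equal to assigned dose over assigned interval; the documents state neither how often delays occur nor what planned duration means. The consequence is confined to descriptive tolerability output. The correction should be made, but no dose-finding or efficacy conclusion rests on it.

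**What to change.** Reconcile SAP 2.5.1.1 with Protocol 10.3, as follows:

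1. For each drug, set PDI = protocol-assigned dose / assigned dosing interval in days. For weight-based dosing, use assigned mg/kg times the weight used for dosing.
2. Set RDI = (actual cumulative dose / duration of exposure to that drug) / PDI, and use this in SAP 2.8.5.
3. Define the last date of exposure per drug. The SAP relies on it ("Duration of exposure to study drug (weeks): (last date of exposure to study drug") but gives dates only for study treatment as a whole.
4. State the sponsor's chosen conventions for schedule changes (Protocol 6.1.1), intra-patient escalation (6.2.3.2), switches to combination (6.2.3.2.1), and a last interval cut short by death or cut-off.
5. Put RDI and its categories on one scale, percent or ratio.
6. Either summarise DI as Protocol 10.3 says or declare the change.
7. In SAP 2.5.3, keep mg infused over mg prescribed if that is what is wanted, but call it compliance.

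The cost is one revised derivation and a few written conventions. Beyond the dosing dates and amounts, it needs the assigned dose and interval, the dosing weight, and the dates of any schedule change. Reported RDI will look less favourable for patients with delays.
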